6.1.2 Venetoclax

After ramp-up (see below), venetoclax tablets at the dose 400 mg (4 tablets) should be taken orally once daily with a meal and water, at approximately the same time every day. On days 1-4 of Cycle 1 it is recommended that venetoclax is taken approximately one hour after start of APR-246 infusion. On these days' patients will consume a low-fat meal prior to venetoclax consumption. Starting at cycle 2 venetoclax can be taken before or after start of APR-246 infusion (\pm 2 hours).

During Cycle 1, treatment with venetoclax should start with a ramp-up phase. If no prophylactic antifungal agent is administered concurrently, the ramp-up phase should consist of 100, 200, and 400 mg of venetoclax once daily given on days 1, 2, and 3 of Cycle 1, respectively. For day 4 of Cycle 1 and beyond, the venetoclax dose is 400 mg once daily given in combination with APR-246 with and without azacitidine. If a prophylactic antifungal agent is administered concurrently, the ramp-up and maintenance dose of venetoclax should be determined based on institutional practice and current prescribing information for venetoclax (please see [APPENDIX VIII](#)).

If required, any dosage modifications of venetoclax should be done based on clinical judgement and institutional practice.

Detailed instructions on preparation and administration can be found in the Pharmacy Binder and current package insert.

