- k. Initial response assessment (blasts percentage) is performed on Day 22 (± 3 days). In patients with bone marrow hypocellularity, venetoclax may need to be held and restarted after recovery of blood counts (ANC $\geq 0.5 \times 10^9/L$, and platelets $\geq 25 \times 10^9/L$), confirmed by repeat bone marrow biopsy on approximately Day 35 and following discussion with Medical Monitor. For subjects who

require a delay in study treatment for peripheral blood count recovery after a bone marrow evaluation, hematology values for up to 4 weeks from the bone marrow analysis can be used to determine the IWG response. Ongoing response assessments should be performed at the end of each cycle (every 4 weeks) starting at Cycle 2, based on peripheral blood and bone marrow sample (at the end of even cycles), and peripheral blood sample alone (at the end of odd cycles). After the first year of the study treatment response assessment will be performed every two months. Following a documented CR, a bone marrow aspirate/biopsy is not required if the response assessment can be made based on the peripheral blood, except at the time of suspected relapse at which time a bone marrow aspirate/biopsy is required.

- I. Hematology, including complete blood count with white blood cell differential, weekly. Additional peripheral blood sample should be collected on Day 1 of each cycle starting at Cycle 2 for disease assessment, if bone marrow aspirate is not available.
- m. Serum chemistry, including sodium, potassium, chloride, magnesium, CO₂, blood urea nitrogen (BUN), creatinine, glucose, calcium, albumin, total protein, total bilirubin, AST, ALT, alkaline phosphatase weekly. At screening, the creatinine clearance may be calculated from the serum creatinine. A 24-hour urine for creatinine clearance may be performed at Investigator's discretion.
- n. Serum or urine β hCG must be performed within 7 days prior to study treatment initiation in female patients of childbearing potential.
- o. Standard 12-lead ECGs in triplicate at screening, on Days 1–4 of Cycle 1 and on Days 1 of each subsequent cycle with patient in a semi-recumbent position. Please consult [Table 12](#) for ECG collection schedule.
- p. *Only in cohorts with venetoclax:* Potassium, phosphorus, calcium and uric acid should be evaluated approximately 6–8 hr and 24 hr (\pm 4 hr) after the initial administration of venetoclax in order to monitor for potential development of TLS.

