7.2.2.1 Cycle 1 Days 1-7

Day 1 examinations marked * do not need to be repeated if already performed within 3 days prior to day 1 cycle 1.

- Clinical toxicity assessment
- Concomitant medications review
- Physical examination: Day 1*
- Weight: Day 1*
- ECOG performance status (Day 1*; [APPENDIX III](#))
- Vital signs, including blood pressure, heart rate, respiration rate and temperature, collected 2 hours into APR-246 infusion (\pm 30 min) and at EOI (\pm 30 min)
- Hematology (Day 1*), including complete blood count with white blood cell differential
- Serum chemistry (Day 1*), including sodium, potassium, chloride, magnesium, CO₂, BUN, creatinine, glucose, calcium, albumin, total protein, total bilirubin, AST, ALT, alkaline phosphatase
- ECG: standard 12-lead ECG with patient in a semi-recumbent position; pre-dose (prior to the APR-246 PK blood draw before the infusion) and at the EOI, per [Table 12](#)
- APR-246 administration: Days 1 – 4
- Blood sample for APR-246 pharmacokinetics: on Days 1, 2 and 4, per [Table 9](#)
- *Only in cohorts with venetoclax.* Venetoclax administration: once daily, at approximately the same time every day. On days 1 – 4 it is recommended that venetoclax is taken with a meal and water approximately one hour after start of APR-246 infusion. If no prophylactic antifungal agent is administered concurrently, the ramp-up phase should consist of 100, 200, and 400 mg of venetoclax once daily given on days 1, 2, and 3 of Cycle 1, respectively. If a prophylactic antifungal agent is administered concurrently, the ramp-up and maintenance dose of venetoclax should be determined based on institutional practice and current prescribing information for venetoclax
- *Only in cohorts with venetoclax.* Blood sample for venetoclax pharmacokinetics in the presence of APR-246 ([Table 10](#))
- *Only in cohorts with venetoclax.* TLS lab monitoring: potassium, phosphorus, calcium and uric acid should be evaluated 6 – 8 hr and 24 hr (\pm 4 hr) after the initial administration of venetoclax in order to monitor for potential development of TLS
- Azacitidine administration, *only in cohorts with azacitidine.* Administered daily for 7 consecutive days starting on Day 1 (Days 1 to 7 inclusive). The same route should be maintained over the 7-day treatment period. On Days 1-4 azacitidine is given immediately after APR-246 infusion

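### In venetoclax expansion Cohorts 1-4 the TLS panel is scheduled only around the first ramp-up dose: the later steps have none, and phosphorus and uric acid have no scheduled pre-dose value

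*Combined protocol and SAP*

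**What the plan says.** **TLS panel.** Footnote p of Table 8 (Section 7.1), which applies only to the venetoclax cohorts, opens "Potassium, phosphorus, calcium and uric acid should be evaluated approximately" and gives 6-8 h and 24 h (±4 h). Section 7.2.2.1 sets the same two times "after the initial administration of venetoclax in order to monitor for potential development of TLS". The TLS row of Table 8 is marked on Cycle 1 Days 1 and 2 only. All three places agree.

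**Ramp-up.** Section 6.1.2 says that, with no prophylactic antifungal, "the ramp-up phase should consist of 100, 200, and 400 mg of venetoclax once daily given on days 1, 2, and 3" of Cycle 1, and 400 mg daily continues from Day 4. On timing it says: "On days 1-4 of Cycle 1 it is recommended that venetoclax is taken approximately one hour after start of APR-246 infusion". With an antifungal, "the ramp-up and maintenance dose of venetoclax should be determined based on institutional practice and current prescribing information for venetoclax" (Section 7.2.2.1). The Appendix VIII table gives four steps over Days 1-4: 10, 20, 50 and 70 mg with posaconazole, or a last step of 100 mg with another strong CYP3A inhibitor. For moderate CYP3A or P-gp inhibitors it cuts the dose by at least half.

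**Routine chemistry.** The lists for screening, Day 1, Days 8, 15 and 22, and the weekly checks include potassium, calcium and creatinine. None names phosphorus or uric acid. Footnote m, for example, ends "creatinine, glucose, calcium, albumin, total protein, total bilirubin, AST, ALT, alkaline phosphatase weekly". Day 1 chemistry is among the tests that "do not need to be repeated if already performed within 3 days prior to day 1 cycle 1".

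**The concern.** The protocol raises venetoclax in steps and monitors for TLS, but it ties the monitoring to the lowest step only. Appendix VIII, writing about strong CYP3A inhibitors, places the added TLS risk both at initiation and through the ramp-up. A schedule that stops after the first dose does not match that period.

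Two things are at stake. First, the calendar does not ensure a four-analyte panel after the higher doses, so whether one is drawn depends on the site, the label or a clinical trigger. Second, phosphorus and uric acid on Days 1-2 cannot be read as a change from a scheduled pre-dose value. The Day 1 reference for potassium, calcium and creatinine may itself be up to 3 days old.

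**Working it through.** The plan states no figure on this point to reproduce. The check sets the draw times against the dose times and then goes through the analyte lists.

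**1. Timeline without an antifungal.** Take the first venetoclax dose as hour 0, with doses 24 h apart (Section 6.1.2). Venetoclax is taken about 1 h after the infusion starts, so a pre-infusion draw is about 1 h before that day's dose.

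| Event | Hours from first dose |
|---|---|
| 100 mg, Day 1 | 0 |
| TLS draw 1 | 6-8 |
| TLS draw 2 (24 ±4) | 20-28 |
| 200 mg, Day 2 | 24 |
| Before the Day 3 infusion | 48 − 1 = 47 |
| 400 mg, Day 3 | 48 |
| Before the Day 4 infusion | 72 − 1 = 71 |

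- Latest permitted draw against the 200 mg dose: 28 − 24 = 4 h after it at most.
- Latest permitted draw against the first 400 mg dose: 48 − 28 = 20 h before it.
- TLS panels scheduled after the first 400 mg dose: 0.

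**2. Next scheduled chemistry.** Day 8 ±3 is Day 5 to Day 11. Counted from the 400 mg step on Day 3, that is 5 − 3 = 2 to 11 − 3 = 8 days. It covers two of the four TLS analytes (potassium and calcium) plus creatinine.

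**3. Four-step ramp-up.** The last step is on Day 4, at hour 72. The latest permitted draw is 72 − 28 = 44 h earlier. The third and fourth steps have no panel after them, and the second has at most the 4 h overlap found in step 1.

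**4. Analytes.** Scheduled pre-dose values: potassium, calcium and creatinine yes; phosphorus and uric acid none. Scheduled values after Day 2: phosphorus and uric acid none.

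**5. Where added draws would fall.** Before the Day 3 infusion: 47 − 24 = 23 h after 200 mg. Before the Day 4 infusion: 71 − 48 = 23 h after 400 mg. Both lie within 24 ±4 h. A four-step ramp-up needs one more at 72 + 24 = 96 h, on Day 5. Post-dose panels go from 2 to 2 + 2 = 4 (three steps) or 2 + 3 = 5 (four steps).

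**6. Size of the population.** Section 9.1 gives about 70 expansion patients and a two-stage size of 18 or 33 for Cohort 5, which has no venetoclax. If Cohort 5 takes 18, 70 − 18 = 52 receive venetoclax; if it takes 33, 70 − 33 = 37. If it does not open, the number is higher.

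**The case against.** The strongest objection is that the calendar is not the only source of instructions. Section 6.1.2 says of venetoclax: "Detailed instructions on preparation and administration can be found in the Pharmacy Binder and current package insert". Section 8.1.2.7 refers to a detailed safety plan. Section 2.9.1 and the start of 4.3.2 are not available in the text reviewed. Any of these may already ask for further TLS draws. This stands as a limit: if they do, the edit only brings the calendar into line with them. It does not change what the visible calendar requires.

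Other checks do continue. Toxicity assessment, vital signs and ECGs cover Days 1-4. Section 6.3.7 recommends creatinine before each infusion, and Section 6.3.1 calls for electrolytes if pre-dose QTcF reaches 470 msec. A reader might therefore go too far in saying that patients at 400 mg have no monitoring until Day 8. The documents do not support that; what is missing is a scheduled TLS panel.

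The clinical premise is also narrower than it looks. The visible link between TLS and ramp-up concerns strong CYP3A inhibitors, and no incidence is given. Phosphorus and uric acid can still be read against normal ranges and compared between the two existing draws.

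The lead-in reported no dose-limiting toxicities (DLTs) in 6 + 6 = 12 patients (Synopsis). This is weak reassurance, because TLS that responds to therapy and resolves within 72 h is exempt from the DLT definition (Section 6.1.4) and 12 patients exclude little. The data review team assesses safety after 5 patients have completed a cycle in each expansion cohort (Section 6.1.5). That is a real safeguard, but the text does not say that it adds draws.

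**Conclusion.** The point holds as a gap in the schedule. In Cohorts 1-4, no TLS panel is scheduled after the 400 mg step when no antifungal is given, the later steps of a four-step ramp-up are uncovered too, and phosphorus and uric acid have no scheduled pre-dose value and none after Day 2. It rests on the visible calendar and on once-daily dosing at 24 h intervals.

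It is a worthwhile, low-cost safety improvement. Its clinical effect cannot be quantified from the documents, and confidence is medium because of the material that could not be checked.

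A reader might take 37 or 52 as the number of patients who would reach 400 mg without a panel. The documents do not support that. Those are totals of venetoclax expansion patients under an assumed Cohort 5 size of 33 or 18. They include patients on an antifungal, and a patient on a strong CYP3A inhibitor under the Appendix VIII table would stay at 70 or 100 mg. The number without an antifungal and the number already treated are both unknown.

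**What to change.** For the venetoclax cohorts, amend Section 7.2.2.1, the Table 8 TLS row and footnote p to read:

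*Potassium, phosphorus, calcium, uric acid and creatinine before the first APR-246 infusion on Cycle 1 Day 1, 6-8 hr and 24 hr (±4 hr) after the first venetoclax dose, and 24 hr (±4 hr) after each subsequent ramp-up dose; results to be reviewed before the next venetoclax dose.*

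In practice this means pre-infusion draws on Days 3 and 4, plus Day 5 for a four-step ramp-up. Tying the first draw to the infusion avoids a baseline taken while APR-246 is running. The review clause means that each 24 h sample has to be taken before that day's dose. A pre-infusion draw leaves about 1 h, so a site with a slower laboratory would draw earlier in the window or give venetoclax later. The Day 8 visit should stay where it is so that weekly chemistry is kept.

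**Cost.** One pre-infusion panel on Day 1, creatinine added to the two existing draws, and two further panels at infusion visits already scheduled. The Day 1 and Day 4 samples can share the pre-infusion APR-246 PK draw (Table 9). Day 3 has no PK draw, so its sample goes with the recommended creatinine. The 6-8 h sample can share the 6 h or 8 h venetoclax PK draw (Table 10). Only a four-step ramp-up may need an extra attendance, on Day 5, in Cohorts 1 and 3, or in Cohorts 2 and 4 if azacitidine is paused that day. The change applies to patients who have yet to start Cycle 1.

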7.2.2.2 Cycle 1 Day 8 (± 3 Days)

- Clinical toxicity assessment
- Concomitant medications review
- Hematology, including complete blood count with white blood cell differential
- Serum chemistry, including sodium, potassium, chloride, magnesium, CO₂, BUN, creatinine, glucose, calcium, albumin, total protein, total bilirubin, AST, ALT, alkaline phosphatase
- *Only in cohorts with venetoclax.* Venetoclax administration: 400 mg (4 tablets) once daily, at approximately the same time every day, with a meal and water. If a prophylactic antifungal agent is administered concurrently, the daily dose of venetoclax should be determined based on institutional practice and current prescribing information for venetoclax

7.2.2.3 Cycle 1 Day 15 (± 3 Days)

- Clinical toxicity assessment
- Concomitant medications review
- Hematology, including complete blood count with white blood cell differential
- Serum chemistry, including sodium, potassium, chloride, magnesium, CO₂, BUN, creatinine, glucose, calcium, albumin, total protein, total bilirubin, AST, ALT, alkaline phosphatase
- *Only in cohorts with venetoclax.* Venetoclax administration: 400 mg (4 tablets) once daily, at approximately the same time every day, with a meal and water. If a prophylactic antifungal agent is administered concurrently, the daily dose of venetoclax should be determined based on institutional practice and current prescribing information for venetoclax

7.2.2.4 Cycle 1 Day 22 (± 3 Days)

- Clinical toxicity assessment
- Concomitant medications review
- Hematology, including complete blood count with white blood cell differential
- Serum chemistry, including sodium, potassium, chloride, magnesium, CO₂, BUN, creatinine, glucose, calcium, albumin, total protein, total bilirubin, AST, ALT, alkaline phosphatase
- *Only in cohorts with venetoclax.* Blood sample for venetoclax pharmacokinetics in the presence of APR-246 ([Table 10](#))
- Bone marrow sample for response assessment (blasts percentage). In patients with bone marrow hypocellularity, venetoclax may need to be held and restarted after recovery of blood counts (ANC $\geq 0.5 \times 10^9/L$, and platelets $\geq 25 \times 10^9/L$), confirmed by repeat bone marrow biopsy on Day 35 and following discussion with Medical Monitor.

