--	--

	
any cause, whichever occurs first. Patients alive with no progressive disease will have their DOR censored at the date of the last clinical assessment. The duration of CR will be summarized in each treatment arm by providing duration of complete response (DOCR) and duration of overall response (DOR), using Kaplan-Meier methodology. DoR endpoints will not be formally compared between treatment arms.
 
Overall response will be summarized in number (%) of patients in each category of responses and ORR will be analyzed by using the similar method as CR rate.
 
Survival data are collected at treatment and follow-up periods. Patients will be followed until death or withdrawal of consent for study participation. Overall survival (OS) is defined as the number of days from the first day of treatment to the date of death. Kaplan-Meier methodology will be utilized.
 
Progression-free survival (PFS) is defined as the time from the first day of treatment to disease progression or death from AML, whichever occurs first. If neither event occurs, PFS will be censored at the date of the last clinical assessment. Kaplan-Meier methodology will be utilized.
 
Safety Analyses
 
Safety data including AEs, vital signs, laboratory data, electrocardiogram (ECG), physical exam will be tabulated for the safety population. AEs will be tabulated by System Organ Class (SOC), preferred term, severity, and relationship to treatments. The tabulation of laboratory parameters will include the normal ranges for each parameter. Each value will be classified as falling above, below, or within the normal range. Laboratory parameters will also be tabulated by maximum NCI CTCAE v5.0 severity grade.
 
Pharmacokinetic Analysis
 
PK sampling for APR-246 are performed in Cycle 1, on Days 1, 2 and 4, and on Day 4 of every subsequent cycle.
 
PK sampling for venetoclax is performed on Days 1, 2, 22 and 23 of Cycle 1 and on Day 4 of Cycles 2 – 5.
 
Non-compartmental or population pharmacokinetic methods will be used to derive APR-246 and venetoclax PK parameters (C_{max}, T_{max}, AUC, V_d and CL).
 
The pharmacokinetics of APR-246 and venetoclax will be summarized using descriptive statistics (mean, standard deviation, CV% mean, geometric mean, CV% geometric mean) and compared with historical control data.
 
APR-246 AUC and C_{max} will then be tested for association with signs of efficacy and safety. If an observable trend exists, a PK/PD model will be developed to evaluate the exposure-response relationship between APR-246 plasma exposure and outcome measures in the presence of venetoclax. Demographic and clinical data (ethnicity, current age, body weight, sex, disease status, etc.) will be utilized to assess interpatient variability in the PK and PK/PD relationships.

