6.1.1 APR-246

APR-246 is administered as a 6-hour IV infusion daily on Days 1–4 of each 28-day cycle. APR-246 fixed dose is 4.5 g. APR-246 is administered in a 2-step infusion:

Step 1: Loading dose of 1.5 g for the first 45 minutes (\pm 2 min)

Step 2: Maintenance dose of 3 g over 5 hours 15 minutes (\pm 30 min)

In each portion of the study, if patients develop intolerable toxicity(ies) to APR-246 in combination with venetoclax and azacitidine, the dose of APR-246 may be reduced (please consult Section 4.1 and [Table 2](#)).

APR-246 vials are to be stored at 2-8°C (35.6-46.4°F). At the pharmacies and at the study centers, the prepared APR-246 study product (diluted in sodium chloride solution) is to be stored at not more than 25°C. The infusion should be completed within 24 hours from the time of preparation.

Detailed instructions on vial concentration, preparation and dispensing can be found in the Pharmacy Binder. The infusion timing, including start/stop times and the time of rate change, must be recorded.

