6.4 Concomitant Treatment

Patients must not receive any other concurrent anti-cancer therapy, including investigational agents while on study treatment. Please also see Section 2.3, regarding known drug-drug interactions for venetoclax, and the importance of avoiding certain food such as grapefruits. This is important both for patient safety and for enabling a correct assessment of an unlikely drug-drug interaction between the study drug APR-246 and venetoclax. For patients concomitantly treated with strong or moderate CYP3A inhibitors, or P-gp inhibitors, the dose of venetoclax should be determined based on institutional practice and current prescribing information. Strong or moderate CYP3A inducers should be avoided (see [APPENDIX VIII](#)).

Patients may continue their baseline medication(s) as long as they are not prohibited. Palliative and supportive care (e.g., anti-emetics, bisphosphonates) for disease-related symptoms will be offered to all patients in the study per institutional practices. AEs will be treated as clinically indicated. All concomitant medications that are currently in use or that become necessary during the study should be recorded.

If the patient develops an acute infusion reaction (\geq Grade 2), the infusion must be stopped until the reaction is resolved to \leq Grade 1. Premedication (e.g., systemic corticosteroids) may be used after the first cycle.

Use of myeloid growth factors is allowed at the discretion of the investigator per institutional practices. If patients experience prolonged myelosuppression, they should be placed on infection prophylaxis per standard of care.

Hydroxyurea may be used for control of leukocytosis.

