7.2.3.1 Cycle 2 Days 1-7

- Clinical toxicity assessment
- Concomitant medications review
- Vital signs, including blood pressure, heart rate, respiration rate and temperature, collected 2 hours into APR-246 infusion (± 30 min) and at EOI (± 30 min)
- *Only in cohorts with venetoclax.* Venetoclax administration: 400 mg (4 tablets) once daily, at approximately the same time every day, with a meal and water. If a prophylactic antifungal agent is administered concurrently, the daily dose of venetoclax should be determined based on institutional practice and current prescribing information for venetoclax. *Note:* Day 4 of Cycles 2-5 only: Blood sample for venetoclax pharmacokinetics in the presence of APR-246 ([Table 10](#))
- APR-246 administration: Days 1 – 4
- Azacitidine administration, *only in cohorts with azacitidine.* Administered daily for 7 consecutive days starting on Day 1 (Days 1 to 7 inclusive). The same route should be maintained over the 7-day treatment period. On Days 1-4 azacitidine is given immediately after APR-246 infusion
- Blood sample for APR-246 pharmacokinetics: on Day 4, per [Table 9. Samples for APR-246 to be taken 1-3 hours after completion of APR-246 administration.](#)

- ECG: standard 12-lead ECGs with patient in semi-recumbent position prior to the PK blood draw before APR-246 infusion on Day 1, per [Table 12](#)

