8.4 Pharmacokinetics

Plasma concentrations of APR-246 will be measured in Cycle 1, at the timepoints provided in [Table 9](#). Please refer to sections [2.3](#) and [6.4](#), regarding the risk of certain drugs and foods influencing the PK of venetoclax such as grapefruits (see [APPENDIX VII](#)). This is important both for patient safety and for enabling a correct assessment of an unlikely drug-drug interaction between the study drug APR-246 and venetoclax from PK samples.

Table 9. PK Blood Sampling Timepoints for APR-246

APR-246 plasma collection timepoints ^a	Cycle 1			Subsequent Cycles
	D1	D2	D4	D4
Prior to APR-246 infusion	×	×	×	×
At the end of APR-246 infusion	×		×	×
1 hour after the end of APR-246 infusion	×		×	× ^c
3 hours after the end of APR-246 infusion ^b	×			

^a A window of ±15 min applies to each time point.

^b Samples are collected as part of the venetoclax PK sampling scheme below ([Table 10](#)). A single PK sample should be drawn and split into 2 samples for analysis of both drugs at these timepoints.

^c Sample collected between 1 and 3 hours after the end of infusion.

Only in cohorts with venetoclax, plasma concentrations of venetoclax will be measured in Cycle 1, at the timepoints provided in [Table 10](#), and then prior to venetoclax administration on Day 4 of Cycles 2 – 5 ([Table 11](#)).

Table 10. PK Blood Sampling Timepoints for Venetoclax in Cycle 1

Venetoclax plasma collection timepoints	D1	D2	D22	D23
Prior to venetoclax administration ^a	×	×	×	×
2 hours following venetoclax administration ^b	×		×	
3 hours following venetoclax administration ^c	×		×	
4 hours following venetoclax administration ^d	×		×	

6 hours following venetoclax administration ^e	×		×	
8 hours following venetoclax administration ^f	×		×	

^a Baseline sample collected prior to venetoclax administration. On Day 1, it is recommended that venetoclax is given 1 hour after the start of APR-246 infusion (± 10 min), following a meal that will start approximately 15 minutes after initiation of APR-246 infusion. On Day 1, the baseline sample prior to APR-246 infusion can be split into two samples and used as pre-dose sample for venetoclax as well.

^b 3 hours following initiation of APR-246 infusion on Day 1 (± 15 min)

^c 4 hours following initiation of APR-246 infusion on Day 1 (± 15 min)

^d 5 hours following initiation of APR-246 infusion on Day 1 (± 15 min)

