9.6 Pharmacokinetic Analysis

The pharmacokinetics of APR-246 and venetoclax will be summarized using descriptive statistics (mean, standard deviation, CV% mean, geometric mean, CV% geometric mean) and compared with historical control data.

APR-246 and venetoclax concentrations will be determined, and PK parameters (C_{max} , T_{max} , AUC, V_d and CL) will be derived using population pharmacokinetic or non-compartmental methods.

APR-246 concentrations will be determined by a validated high-performance liquid chromatography (HPLC) tandem mass spectrometry (LC/MS/MS) method. A population PK model will be used to estimate PK parameters C_{max} , AUC and CL for each individual patient. APR-246 AUC and C_{max} will then be tested for association with signs of efficacy and safety in the presence of venetoclax. If an observable trend exists, a PK/PD model will be developed to evaluate the exposure-response relationship between APR-246 plasma exposure and outcome measures. Demographic and clinical data (ethnicity, current age, body weight, sex, disease status, etc.) will be utilized to assess interpatient variability in the PK and PK/PD relationships.

APR-246 PK parameters will be compared to historical controls for the assessment of drug-drug interactions.

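### The Cycle 1 Day 22 venetoclax sample is labelled as taken with APR-246 but falls 15–21 days after it, and Section 9.6 leaves unused a same-patient trough comparison that the trial already samples

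*Combined protocol and SAP*

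**What the plan says.** **Dosing.** Section 6.1.1: "APR-246 is administered as a 6-hour IV infusion daily on Days 1–4 of each 28-day cycle".

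**Sampling.** The synopsis (Pharmacokinetic Analysis) states "PK sampling for APR-246 are performed in Cycle 1, on Days 1, 2 and 4, and on Day 4 of every subsequent cycle", so no APR-246 concentration is measured on Day 22 or 23. For the other drug it states "PK sampling for venetoclax is performed on Days 1, 2, 22 and 23 of Cycle 1". Table 10 gives venetoclax profiles to 8 h on Days 1 and 22, and a pre-dose sample only on Days 2 and 23. Section 8.4 continues the sampling "then prior to venetoclax administration on Day 4 of Cycles 2 – 5", one trough per cycle (Table 11).

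**Label.** Section 7.2.2.4 calls the Day 22 draw "Blood sample for venetoclax pharmacokinetics in the presence of APR-246". Section 7.2.3.1 uses the same words for the later cycles: "Day 4 of Cycles 2-5 only: Blood sample for venetoclax pharmacokinetics in the presence of APR-246".

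**Purpose and analysis.** Section 6.4 says that avoiding interfering foods and drugs matters "for enabling a correct assessment of an unlikely drug-drug interaction between the study drug APR-246 and venetoclax", and Section 8.4 ties the same aim to the PK samples. Section 9.6 opens by comparing the PK of both drugs with historical data. Its one sentence on interactions reads "APR-246 PK parameters will be compared to historical controls for the assessment of drug-drug interactions" and so concerns APR-246 exposure, not venetoclax. Section 9.6 allows population PK or non-compartmental methods. It names no within-patient venetoclax comparison and does not list APR-246 presence as a covariate.

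**The concern.** One phrase is attached to two opposite conditions. On Day 4 of Cycles 2–5 it is accurate. On Day 22 it contradicts the dosing schedule, and with no APR-246 sample that day the data could not settle the matter.

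The analysis gap matters more than the label. The protocol wants the PK samples to support a sound view of whether APR-246 alters venetoclax exposure, but the only comparator named for venetoclax is historical. A difference from historical data could reflect an interaction, or it could reflect population, co-medication, food or assay. A patient serving as their own control removes most of these alternatives, and the trial already draws the samples. At stake is how well the secondary PK objective can address an interaction; the primary safety endpoints and the Simon two-stage design are untouched.

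**Working it through.** The documents give no sample size or precision for any PK comparison, so there is no planned figure to reproduce.

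**1. Is APR-246 present on Day 22?** Inputs: last infusion on Day 4, lasting 6 h (Section 6.1.1); Day 22 window ±3 days (Section 7.2.2.4). Hours from end of infusion = (day − 4) × 24 − 6.

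- Day 19: 15 × 24 − 6 = 354 h
- Day 22: 18 × 24 − 6 = 426 h
- Day 25: 21 × 24 − 6 = 498 h

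The gap is therefore 15–21 days. No APR-246 half-life is visible, so a range is needed. At the earliest day, the residual fraction exp(−ln2 × 354/t½) is 0.004% for t½ = 24 h and 0.6% for 48 h. It stays at or below 1% for half-lives up to 354 × ln2/ln100 ≈ 53 h.

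**2. Is Day 1 taken with APR-246?** Yes. Venetoclax is taken 1 h after the infusion starts, so the 2, 3, 4, 6 and 8 h samples fall at 3, 4, 5, 7 and 9 h from infusion start. The last two are 1 h and 3 h after a 6-h infusion, as the Table 10 footnotes say.

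**3. Could Day 1 be set against Day 22?** Not as an interaction contrast. Inputs: 100 mg on Day 1 and 400 mg by Day 22 without an antifungal (Section 6.1.2); half-life about 26 h (Section 2.3); one-compartment linear kinetics assumed.

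- Accumulation R = 1/(1 − exp(−ln2 × 24/26)) = 2.12
- Dose ratio = 400/100 = 4
- Expected 24-h exposure ratio with no interaction = 4 × 2.12 ≈ 8.5; dose-normalised, about 2.1

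With an antifungal the doses differ (Section 6.1.2, Appendix VIII), so 8.5 applies only to patients without one.

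**4. Which samples can be paired?** Pre-dose on Cycle 1 Day 22/23 (no concurrent APR-246) and pre-dose on Day 4 of Cycles 2–5 (after infusions on Days 1, 2 and 3). At the same venetoclax dose and at steady state, the expected ratio without an interaction is 1. Section 2.3 describes venetoclax kinetics as stable over time, which supports comparing across cycles.

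**5. What weakens the pairing?**

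- *Incomplete shift.* If clearance changed fully from Day 1, the fraction of the move to a new steady state reached after three days is 1 − exp(−ln2 × 72/26) = 0.85. An effect limited to the 6-h infusion would be diluted further.
- *Interruptions.* Section 7.2.2.4 allows venetoclax to be held after Day 22, and Section 4.1 allows 14–21-day venetoclax cycles. After a hold of 7–14 days with restart on Cycle 2 Day 1, the Day 4 trough is about 0.85 of steady state, a spurious ratio of about 0.85.
- *Azacitidine.* It is given on Days 1–7 (Section 6.1.3), so in triplet patients Day 4 differs from Day 22 by two drugs.

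**6. Precision.** 90% CI around a ratio of 1 = exp(±t₀.₉₅,ₙ₋₁ × √ln(1 + CV²) × √(2/n)), with one sample per condition. The within-patient CV is an assumption. For n = 12 and CV = 30%: exp(±1.796 × 0.294 × 0.408) = 0.81–1.24.

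| Pairs | CV 30% | CV 50% |
|---|---|---|
| 6 | 0.71–1.41 | 0.58–1.73 |
| 12 | 0.81–1.24 | 0.71–1.41 |
| 30 | 0.88–1.14 | 0.81–1.23 |

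**The case against.** The best defence is that nothing in the analysis depends on the label. It is visit-checklist wording; Section 8.4 and Table 10 do not carry it, and Section 9.6 defines no arm with or without APR-246. The secondary objective is a PK profile, not an interaction test. The protocol regards an interaction as unlikely, and the lead-in RP2Ds were set from DLTs. Population PK, already permitted, can handle dose and accumulation. The paired trough cannot deliver the venetoclax endpoints (Tmax, Cmax, AUC), and from Cycle 2 venetoclax may be taken up to 2 h either side of the infusion start, so the timing of the trough varies.

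Most of this stands, and it limits the point. A reader might infer that Day 22 will be analysed as the interaction arm, or that the plan carries an 8.5-fold error. The documents support neither: no section proposes Day 1 against Day 22, so that figure only warns against a comparison someone might later make. Nor is the paired trough a complete interaction test.

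What remains is that the Day 22 label is wrong against the dosing schedule, and that the permitted population PK is not said to include APR-246 presence. The one comparator stated for venetoclax is therefore historical, although a comparison less exposed to between-study bias is available from samples already planned.

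**Conclusion.** The point holds in limited form. The label is an editorial error. The unspecified within-patient comparison is a worthwhile, cheap improvement to a secondary PK analysis.

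The comparison would be supportive only. It gives no estimate of Cmax, Tmax or AUC under APR-246 at steady state, and it may understate an effect because three days reach only about 85% of a new steady state. With 12 usable pairs it could not exclude changes of roughly 20–25% at an assumed CV of 30%, or 30–40% at 50%.

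The conclusion assumes negligible APR-246 by Day 19–25, one-compartment linear venetoclax kinetics with a 26-h half-life, and matched, uninterrupted venetoclax dosing at both samples. The section on the venetoclax and APR-246 dose rationale (2.8.3) is redacted, so any reasoning given there could not be considered.

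**What to change.** - In Section 7.2.2.4, relabel the Day 22 sample, and describe Day 23 likewise, as venetoclax without concurrent APR-246. In Section 7.2.3.1, point the Cycle 2–5 Day 4 sample to Table 11 instead of Table 10.
- In Section 9.6, add a supportive analysis: the within-patient geometric mean ratio, with 90% CI, of venetoclax pre-dose concentration on Day 4 of Cycles 2–5 against Cycle 1 Day 22/23. Alternatively, name APR-246 presence as a covariate in a venetoclax population PK model.
- Restrict the paired analysis to patients with the same venetoclax dose, unchanged CYP3A/P-gp co-medication and no venetoclax interruption before either sample.
- Make the doublet cohorts (APR-246 + venetoclax) the primary set and report the triplet cohorts separately, because azacitidine overlaps Day 4.
- State that Day 1 against Day 22 is not an interaction contrast, because dose and accumulation differ.

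The cost is protocol and SAP wording plus a short analysis, with no new samples or visits. The price is a trough-only answer from a subset that shrinks with holds and antifungal changes. The comparison of APR-246 parameters with historical controls is unaffected: both drugs start on Cycle 1 Day 1, so APR-246 has no venetoclax-free period within these patients.
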